6. STUDY ASSESSMENTS AND PROCEDURES

This Section provide an outline of the time and completing of all study procedures and a description of specific procedures. A schedule of Time and Events is provided in [Table 5](#)

Table 5 Time and Events Table

Detailed procedure and time window please reference to SPM.

Visit	Visit 0 (Pre-Screen)	Screening Visit (Visit 1)	Double-blind treatment period									Early Withdrawal (EW) Visit	Follow-Up (Phone contact)
			Visit 2	Visit 3	Visit 4	Visit 5	Visit 6	Visit 7	Visit 8	Visit 9			
Day		Day -7 to -14	Day 1	Day 2	Day 28±2	Day 56±4	Day 84±4	Day 112±4	Day 168±4	Day 169 (Visit 8 +1 day)			7±2 days after Visit 9 or EW
Week		-1	0	0	4	8	12	16	24				
Written Informed Consent ¹	X												
Demography/ COPD History	X												
Medical History		X											
Physical Examination		X								X		X	
Smoking Status		X								X		X	
Smoking Cessation Counselling		X								X		X	
Chest X-ray ²	X												
Inclusion/exclusion criteria		X											
Randomization criteria			X										
Screening spirometry (including post-bronchodilator testing) ³		X											
mMRC questionnaire		X											
Register visit in IWRS ⁴ (RAMOS NG)			X		X	X	X	X					
Diary Card Dispense or Collection/Review		X	X	X	X	X	X	X	X	X		X	

Visit	Visit 0 (Pre-Screen)	Screening Visit (Visit 1)	Double-blind treatment period									Early Withdrawal (EW) Visit	Follow-Up (Phone contact)
			Visit 2	Visit 3	Visit 4	Visit 5	Visit 6	Visit 7	Visit 8	Visit 9			
Day		Day -7 to -14	Day 1	Day 2	Day 28±2	Day 56±4	Day 84±4	Day 112±4	Day 168±4	Day 169 (Visit 8 +1 day)			7±2 days after Visit 9 or EW
Week		-1	0	0	4	8	12	16	24				
Efficacy assessments													
Trough Spirometry ⁵				X	X	X	X	X	X	X			
Serial Spirometry ⁶			X										
COPD exacerbation assessment	X	X	X	X	X	X	X	X	X	X			X
Baseline Dyspnea Index (BDI)			X										
Transition Dyspnea Index (TDI)					X		X		X				
SGRQ			X		X		X		X				
COPD Assessment Test (CAT)			X		X		X		X				
Healthcare resource utilization ⁷													
Safety Assessments													
12-Lead ECG ⁸		X	X ⁸				X ⁸		X ⁸		X		
Vital Signs (blood pressure and pulse rate) ⁹		X	X	X	X	X	X	X	X	X	X		
Adverse Event			X	X	X	X	X	X	X	X	X		X
Serious Adverse Event /Con-Med Assessment	X	X	X	X	X	X	X	X	X	X	X		X
Laboratory Assessments													
Routine urine		X							X		X		
Urine Pregnancy Test		X	X				X		X		X		X
Clinical Laboratory tests ¹⁰		X					X		X		X		
Medication													

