6.2.7. COPD Exacerbations

A COPD exacerbation will be defined as an acute worsening of symptoms of COPD requiring the use of any treatment beyond study medication or rescue albuterol/salbutamol. This includes requiring the use of antibiotics, systemic corticosteroids, and/or emergency treatment or hospitalization. COPD exacerbations will be recorded on the COPD exacerbation page of the eCRF.

Subjects who experience an exacerbation during treatment or run-in period requiring the use of any systemic/oral corticosteroids, with/without either prescribed or non-prescribed (self administered) antibiotics, and/or emergency treatment or hospitalisation will be withdrawn from the study and will not be allowed to re-screen. However, subjects who experience a COPD exacerbation/lower respiratory tract infection requiring only the use of antibiotics, either prescribed or non-prescribed (self-administered), may continue to participate in study.

COPD exacerbations are associated with the disease under study and will not be recorded as AEs unless the exacerbation meets the definition of a “serious” AE as defined in Section 6.3.5.2 of this protocol. Exacerbations that meet the definition of “serious” AEs will be recorded on the appropriate eCRF section and should be reported to GSK for all study subjects regardless of whether or not they are randomized to study medication.

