8.3.1. Analysis Populations

Four subject populations will be identified.

The **All Subjects Enrolled** Population will comprise all subjects, for whom a record exists on the study database, including screen failures and any subject who was not screened but experienced an SAE between the date of informed consent and the planned date of the Screening Visit. This population will be used for reporting subject disposition, reasons for withdrawal prior to randomization, and inclusion, exclusion and randomization criteria deviations and SAEs for non-randomized subjects.

The **Screen and Run in Failure** population will comprise all subjects in the All Subjects Enrolled Population who are recorded as screen failures or run-in failures in the electronic case report form (eCRF). It will be used for the tabulation of reasons for screen and run-in failure and for inclusion, exclusion and randomisation criteria failed.

The Modified **Intent-to-treat** (ITT) Population will comprise all subjects randomized to treatment who received at least one dose of randomized study medication in the treatment period. Randomized subjects will be assumed to have received study medication unless definitive evidence to the contrary exists. Outcomes will be reported according to the randomized treatment allocation. This population will constitute the primary population for all data analyses and displays. All scheduled data collected until the time of study discontinuation will be included in the Modified Intent-to-treat analysis for subjects who withdraw from the study.

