7.3.2.4. Rescue Salbutamol Use (mean puffs/days)

| Statistical Analyses |
|--|
| Endpoint(s) |
| 
 Rescue Salbutamol Use (mean puffs/days) (absolute and change from baseline value) |
| Model Specification |
| 
ANCOVA model
 
 The mean number of puffs of rescue medication per day over each four weeks of treatment and the entire 24 week treatment period will be analyzed. Terms in model: 
 Response : Rescue Salbutamol Use (mean puffs/days) (absolute or change from baseline value) Fixed Categorical : Treatment, Smoking Status, Country^[1] Fixed Continuous Covariates : Baseline Baseline is defined in Section 10.6.5 Rescue Use part. Two models will be fitted; one with absolute value and one with change from baseline value. |
| Model Checking & Diagnostics |
| 
 Refer to Appendix 12: Model Checking and Diagnostics for Statistical Analyses. |
| Model Results Presentation |
| 
 LS means and LS mean change from baseline values for each treatment group will be presented with their associated standard errors. Estimated treatment differences along with corresponding 95 % CIs and p-values will be presented for the treatment comparisons. |
| Example SAS code |

| Statistical Analyses |
|----------------------|
|----------------------|

```

proc mixed data=start;
  by week;
  class treatment smokehis country[1];
  model endpoint=treatment baseline smokehis country[1];
  lsmeans treatment / cl diff e om;
  ods output lsmeans=lsmeans;
  ods output diffs=diffs;
run;

```

Note: [1]: In China subgroup analysis, Country will be removed.

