t_f represents the actual relative time at the first timepoint ($t_f = 0$ as the pre-dose measurement is used),

t_l represents the actual relative time at the last timepoint (the 6h timepoint),

I represents the number of timepoints used in the AUC calculation.

If missing values are present in data required for the calculation of the weighted means, the following approach will be employed:

- If more than a third of the observations are missing then the weighted mean will be set to missing for that subject.
- If an observation is missing between two non-missing observations, the value will be interpolated between the two non-missing values.
- If there are two or more missing points that occur consecutively then the weighted mean will be set to missing.
- If the first time-point is missing then the weighted mean will be set to missing.
- If the last time-point is missing then the weighted mean will be set to missing.

Rescue Use

- For rescue use, 'day' refers to the period (24 hours) between one record of rescue use and the next in the database.
- The total puffs of rescue for each day will be calculated as number of salbutamol puffs. If the number of puffs are missing then the total puffs will be set to missing for that day.
- Rescue use will be summarised over the periods defined in below table:

| Period | First day | Last day |
|----------|---|----------------|
| Baseline | Latest of 6 days before Visit 2 and day after Visit 1 | Day of Visit 2 |
| Week 1-4 | Study day 2 (day after Visit 2) | Study day 29 |
| Week 5-8 | Study day 30 | Study day 57 |

| Rescue Use | | | |
|---|---------------------------------|--|--|
| Week 9-12 | Study day 58 | Study day 85 | |
| Week 13-16 | Study day 86 | Study day 113 | |
| Week 17-20 | Study day 114 | Study day 141 | |
| Week 21-24 | Study day 142 | Earliest of Study day 169 and day before Visit 9 | |
| Week 1-24 | Study day 2 (day after Visit 2) | Earliest of Study day 169 and day before Visit 9 | |
| 
 For each summary period, the mean number of puffs per day and the percentage of rescue-free days will be calculated, provided at least half the days within the summary period have non-missing values for the endpoint. Any data recorded after study day 169 (but before Visit 9) will not be included in any summaries. | | | |

| Time to Onset on Day 1 |
|--|

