10.7.2.4. Handling of Missing Data for Statistical Analysis

| Element | Reporting Detail |
|------------------------------|--|
| MMRM | 
 ● Missing data will not be directly imputed in this analysis; however, all non-missing data for a subject will be used within the analysis to estimate the treatment effect |
| ANCOVA | 
 ● For analysis of trough FEV1 at Day 169, sensitivity analyses with LOCF to imputed missing data will be produced for supportive analysis. ● Missing data will not be imputed for other analysis. |
| Cox's proportional Analysis | 
 ● Missing data will not be imputed. |
| Logistic regression Analysis | 
 ● Missing data will not be imputed. |

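### The Week 1–24 rescue-use analysis omits subjects who withdraw before about Day 85, although their diary data are collected and enter the 4-week analyses

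*SAP*

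**What the plan says.** SAP 10.6.5 (Rescue Use) lists seven on-treatment periods: six of four weeks, and Week 1–24. Week 1–24 starts on Study day 2 and ends on the "Earliest of Study day 169 and day before Visit 9". A period's mean puffs per day and percentage of rescue-free days are derived "provided at least half the days within the summary period have non-missing values for the endpoint". Nothing in the definition ends a period at withdrawal.

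SAP 7.3.2.4 fits separate ANCOVAs to mean puffs per day, which "over each four weeks of treatment and the entire 24 week treatment period will be analyzed". The percentage of rescue-free days is summarised but not modelled (SAP Table 5). On missing values, SAP 10.7.2.4 reserves LOCF for trough FEV1 at Day 169 and adds, for ANCOVA, "Missing data will not be imputed for other analysis".

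On withdrawn subjects, Protocol 8.3.1 says "All scheduled data collected until the time of study discontinuation will be included in the Modified Intent-to-treat analysis for subjects who withdraw", and SAP section 4 repeats this. Protocol 6.2.7 states that subjects whose exacerbation needs systemic or oral steroids, emergency treatment or hospitalisation "will be withdrawn from the study and will not be allowed to re-screen"; exacerbations treated with antibiotics alone may continue. Under Protocol 4.5, permanently stopping study drug also means leaving the study, so diary recording ends there.

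**The concern.** The half-of-days rule looks like an ordinary completeness check, but over a period that keeps its full length after withdrawal it also acts as a retention requirement. A subject can have an unbroken diary for nearly 12 weeks and still have no Week 1–24 value. The result labelled as the whole treatment period then describes only subjects with at least about 12 weeks of recorded data.

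This matters because leaving is partly tied to the course of the disease. Withdrawal is compulsory after the more serious exacerbations, and rescue use may well differ in the weeks before one. If such subjects differ from those who stay, or leave at different rates in the two arms, the Week 1–24 comparison can be shifted.

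The handling also differs from the rest of the SAP. Trough FEV1, TDI, trough FVC, SGRQ and CAT are all modelled by MMRM with every available visit (SAP 7.1.2, 7.2.2.2, 7.3.2.3, 7.4.2). Mean puffs per day is the one continuous efficacy endpoint followed over 24 weeks that is analysed only by separate ANCOVAs, and it has no missing-data sensitivity analysis.

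**Working it through.** **Inputs.** 288 randomised, 18% withdrawal, about 236 completers (Protocol 4.1). Period limits and the half-of-days rule come from SAP 10.6.5. Visit 8 is on Day 168 ± 4 and Visit 9 one day later, so Days 165 to 173 (Protocol Table 5). The timing of withdrawals and the completeness of diaries are not given.

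**1. The plan's own figure.** 288 × (1 − 0.18) = 236.2, which reproduces the stated 236. Planned withdrawals: 288 × 0.18 = 51.8, about 52.

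**2. Days needed by a withdrawn subject.** With no Visit 9 the period ends on Study day 169.
- Length: 169 − 2 + 1 = 168 days.
- Needed: 168 / 2 = 84 days.
- Day on which an unbroken diary reaches this: 2 + 84 − 1 = Day 85.

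If the diary is 95%, 90% or 80% complete (assumed), the 84th recorded day comes at about Day 90, 95 or 106.

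**3. Completers, for comparison.** With Visit 9 on Day 165 the period is Days 2 to 164, 163 days, needing 82. With Visit 9 on Day 170 or later it is 168 days, needing 84. So 168 days is exact for withdrawn subjects, while completers have 163 to 168.

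**4. What early leavers still contribute.** For a withdrawn subject each 4-week period has 28 days and needs 14. With an unbroken diary:

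| Last diary day | Periods with a value |
|---|---|
| 14 | none |
| 15 | Weeks 1–4 |
| 60 | Weeks 1–4, 5–8 |
| 84 | Weeks 1–4, 5–8, 9–12 |
| 85 | the same three, plus Week 1–24 |

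Only a diary ending before about Day 15 is lost to every rescue analysis.

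**5. How many lack a Week 1–24 value.** Number = 288 × 0.18 × share of withdrawals before Day 85 (assumed).

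| Share early | Subjects | % of 288 |
|---|---|---|
| 25% | 13 | 4.5 |
| 50% | 26 | 9.0 |
| 60% | 31 | 10.8 |
| 70% | 36 | 12.6 |
| 75% | 39 | 13.5 |
| 100% | 52 | 18.0 |

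A constant withdrawal hazard gives 1 − 0.82^(84/168) = 9.4%, about 27 subjects.

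**6. Effect on the treatment difference.** This cannot be calculated. It needs early withdrawal by arm and the rescue use of early leavers after adjustment for baseline, and the documents give neither.

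**The case against.** The strongest defence is that the rule is deliberate and allowed. Protocol 8.3.5 includes withdrawn subjects' data only where possible and leaves the details to the analysis plan. SAP 10.7.1 qualifies both its inclusion rule and its minimum-data rule. The half-of-days rule is an explicit, prespecified condition in that plan, and asking for half the period before calling something a 24-week average is defensible. This stands. A reader might infer that the rule contradicts the Modified ITT statement and that these data must be used; with those qualifiers in place, the two passages are in tension but do not conflict.

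The second defence is that the data are not discarded, since the 4-week ANCOVAs use most of them. This also stands, so it would be wrong to infer that early leavers disappear from the rescue analysis altogether. It does not repair the 24-week estimate, however. Each 4-week model uses only subjects with enough diary in that period, and none of them estimates the average effect over 24 weeks with the early leavers' data included.

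Third, rescue use is listed among the other endpoints, and SAP 10.11 treats comparisons on those as exploratory. No primary or secondary conclusion depends on the rule. This limits how much the point matters.

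**Conclusion.** The point holds for the Week 1–24 summaries and ANCOVA. For a withdrawn subject the rule requires 84 recorded days, which cannot be reached before Day 85. The omission has no imputation or sensitivity analysis behind it. About 26 of 288 subjects are affected if half of the planned withdrawals are early. That share is an assumption; the plan's 18% fixes only the upper limit of about 52.

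A reader might go further and infer that the heaviest users on placebo are removed, so that the benefit is understated. Protocol 1.3 makes this tempting by noting that patients not on active treatment may worsen, as does Protocol 3.2 by giving fewer drop-outs as a reason for 2:1 allocation. The documents do not establish it. They give no withdrawal by arm and no rescue use before withdrawal. The 18% also covers withdrawn consent, loss to follow-up and adverse events, and the ANCOVA already adjusts for baseline rescue use. The omission may be informative; its direction and size are unknown.

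**What to change.** In SAP 7.3.2.4, estimate the 24-week effect on puffs per day from one MMRM fitted to the six 4-week means already derived. Terms: treatment, period, baseline rescue use, smoking status, country (overall analysis only), baseline-by-period and treatment-by-period, with unstructured covariance. Report the treatment difference averaged over the six periods. This follows the trough FEV1 model and keeps the covariates of the current rescue model.

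Keep the Week 1–24 ANCOVA as supportive. State in SAP 10.6.5 that without a Visit 9 the period ends on Study day 169, note there that the half-of-days rule is an exception to the Modified ITT inclusion statement, and report by arm the number of subjects without a Week 1–24 value, for both puffs per day and rescue-free days.

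The cost is SAP wording and one extra model; no new data are needed. The model assumes data are missing at random, so it does not settle losses that the observed diaries cannot explain. It also still omits anyone with fewer than 14 diary days in every period. With withdrawals spread evenly over 168 days and unbroken diaries, that is about 51.8 × 14/168 = 4 of the 26, so about 22 would be brought in.

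Ending the denominator at withdrawal would be simpler, but it would let a few days stand as a 24-week mean with full weight, which is a debatable trade-off.

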10.7. Appendix 7: Premature Withdrawals & Handling of Missing Data

10.7.1. Premature Withdrawals

| Element | Reporting Detail |
|---------|--|
| General | 
 Subject study completion (i.e. as specified in the protocol) was defined as on completion of final on-treatment clinic visit (Visit 9). Withdrawn subjects will not be replaced in the study. All available data from subjects who were withdrawn from the study will be listed and all available planned data will be included in summary tables and figures, unless otherwise specified. In general, the minimum data required will be a baseline evaluation and at least one post-baseline evaluation. If a subject withdraws at a scheduled treatment visit, then any data collected at that visit associated with scheduled visit procedures will be used (under the scheduled visit assignment) in all summaries and analyses wherever possible. All other data collected as part of the early withdrawal at a scheduled visit, or at a standalone EW visit, will only be used in summary or analysis tables as part of the 'worst case post baseline' summary/analysis. Early withdrawal data will be included in any relevant listing. |

10.7.2. Handling of Missing Data

| Element | Reporting Detail |
|----------|--|
| General | 
 For efficacy endpoints, missing data is expected to arise mainly from subjects missing complete visits or time points. The amount of occasional missing data for covariates included in the statistical analysis is expected to be minimal. Missing data will not be directly imputed in primary analysis of each endpoint. For analysis of trough FEV1 at Day 169, sensitivity analyses with LOCF will be produced for supportive analysis. |
| Outliers | 
 Any subjects excluded from the summaries and/or statistical analyses will be documented along with the reason for exclusion in the clinical study report. |

10.7.2.1. Handling of Missing Responder

| Element | Reporting Detail |
|-----------|--|
| Responder | 
 Subjects with missing data and a subsequent non-missing assessment will not be considered a responder or non-responder but will be left as missing. Subjects with missing data and no subsequent assessments will be considered a non-responder. No extra visits will be added and no imputation performed in the original dataset. The analysis dataset will initially contain rows for each visit at which at least one |

| Element | Reporting Detail |
|---------|--|
| | 
derived variable (excluding baseline) is able to be calculated. For these rows, IMPFLAG will be 1 (not imputed).
 
 For subjects who do not provide data at the final visit, additional rows will be created for each subsequent visit after their final visit (i.e. their time of withdrawal) with non-missing data which is planned to be included in the responder analysis. For these rows, IMPFLAG will be 0 (imputed) and responder status will be 'Non-responder'. If the final visit containing non-missing data does not provide enough data to calculate the derived variable on which the responder status is based (e.g. some domains of the SGRQ are present but not all, so the total score cannot be created), then IMPFLAG will be changed to 0 (imputed) and responder status will be 'Non-responder' on that row. Apart from derived FEV1 and FVC, the listings should not contain any rows where all the derived variables are missing, except for the rows which are imputed. (The FEV1 listing may have a blank row between two non-missing rows because all FEV1 derived variables are missing but FVC derived variables are present – IMPFLAG should still be 1 for these rows.) If the baseline value is missing, or there are no post-baseline non-missing assessments, no imputation will be performed No visits will be imputed if they are between two visits with non-missing assessments |

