7.3.2.2. Proportion Endpoints

| Statistical Analyses |
|---|
| Endpoint(s) |
| Model Specification |
| 
 Proportion Achieving Increase in FEV1 of $\geq 12\%$ and ≥ 200 mL above Baseline at any Time During 0-6 h Post-dose on Day 1 Proportion Achieving Increase of ≥ 100 mL above Baseline in Trough FEV1 Proportion of Responders According to TDI Focal Score |
| Proportion Endpoints 
 Logistic Regression Model At each of Days 2, 28, 56, 84, 112, 168 and 169, the proportion of subjects who achieved an increase of 100 mL above baseline in trough FEV1 will be analysed using a separate logistic regression model. At each visit, the proportion of responders according to TDI focal score will be analysed using a separate logistic regression model. Terms in the model: Dependent Variable : Proportion Categorical : Treatment, Smoking Status (screening), Country^[1] Continuous : Baseline FEV1 or BDI |
| Model Checking & Diagnostics 
 Refer to Appendix 12: Model Checking and Diagnostics for Statistical Analyses. |
| Model Results Presentation 
 For each treatment comparison, the odds ratio, 95 % CI and p-value will be presented. |
| Example SAS code <pre>proc logistic data=fevaanal descending; class treatment (ref='1') smokehis country^[1] / param=ref; model respond=treatment base smokehis country^[1] / clodds=wald expb; ods output logistic.oddsratios=odds1 (where=(index(effect,'TREATMENT')>0)</pre> |

| Statistical Analyses |
|---|
| <pre>or index(effect,'treatment')>0)); ods output logistic.parameterestimates=pval1 (keep=probchisq variable classval0 where=(variable in ('TREATMENT', 'treatment'))); run;</pre> |

Note: [1]: In China subgroup analysis, Country will be removed.

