| 
 The time to onset on Day 1 is calculated as the time (both nominal and actual) that the first post-dose FEV1 during the 0-6 h post-dose period is ≥ 100 mL above baseline FEV1. Post-dose assessments that are actually pre-dose will be considered missing in the calculation. Subjects who have at least one FEV1 assessment within the 0-6 h post-dose period but do not achieve a ≥ 100 mL increase from baseline over 0-6 h post-dose will be considered censored. |

| Increase in FEV1 of $\geq 12\%$ and ≥ 200 mL above Baseline at any Time During 0-6 h Post-dose on Day 1 |
|--|
| 
 A flag will be derived to identify whether or not a subject achieved an increase in FEV1 of $\geq 12\%$ and ≥ 200 mL above baseline at any time during 0-6 h post-dose on Day 1. The flag will have values as follows: 
 1, if any FEV1 value recorded at 15 or 30 min, 1, 3 or 6 h was $\geq 12\%$ and ≥ 200 mL above baseline. 0, if no FEV1 value recorded at 15 or 30 min, 1, 3 or 6 h was $\geq 12\%$ and ≥ 200 mL above baseline. |

| Increase of ≥ 100 mL above Baseline in Trough FEV1 |
|--|
| 
 A flag will be derived to identify whether or not a subject achieved an increase of ≥ 100 mL above baseline in trough FEV1 at each of Days 2, 28, 56, 84, 112, 168 and 169. The flag will have values as follows: 
 1, if the trough FEV1 was ≥ 100 mL above baseline. 0, if the trough FEV1 was < 100 mL above baseline, or the trough FEV1 was missing with no subsequent non-missing trough FEV1 values. Missing, if the trough FEV1 was missing but subsequent trough FEV1 values were non-missing. |

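### The non-responder rule in SAP 10.7.2.1 leaves out subjects with no post-baseline assessment, so withdrawals before Day 28 drop out of the TDI, SGRQ and CAT responder denominators

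*SAP*

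**What the plan says.** The responder endpoints that run over several visits (trough FEV1 up by at least 100 mL, TDI, SGRQ, CAT) are analysed by logistic regression. For TDI, SAP 7.3.2.2 states: "At each visit, the proportion of responders according to TDI focal score will be analysed using a separate logistic regression model". SAP 7.4.2 applies the same approach to SGRQ and CAT.

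Missing responder status is handled in several places:

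- SAP 10.7.2.1, general rule: "Subjects with missing data and no subsequent assessments will be considered a non-responder". Rows are added after the subject's last visit with data and flagged as imputed.
- SAP 10.7.2.1, later in the same table: where the baseline is missing, or "there are no post-baseline non-missing assessments, no imputation will be performed".
- SAP 10.6.5, trough FEV1 flag: it is set to 0 when "the trough FEV1 was missing with no subsequent non-missing trough FEV1 values". There is no exception for a subject who never had a post-baseline trough.
- SAP 10.7.1: in general, "the minimum data required will be a baseline evaluation and at least one post-baseline evaluation".
- SAP 10.7.2: "Missing data will not be directly imputed in primary analysis of each endpoint".
- SAP 10.7.2.4, logistic regression: "Missing data will not be imputed".

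The derivations of SGRQ and CAT response (SAP 10.6.4) and TDI response (SAP 10.6.5) all refer to 10.7.2.1 for missing data.

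**The concern.** Counting withdrawals as failures is meant to stop subjects who leave the trial from leaving the comparison. The exception works against that for the earliest leavers. Protocol 4.5 requires withdrawal after an exacerbation treated with systemic steroids, emergency care or hospitalisation, and files COPD exacerbation under lack of efficacy in its list of withdrawal reasons. Some subjects whom the protocol itself classes as efficacy failures would therefore be absent from the responder denominators, purely because the event came before Visit 4.

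If early withdrawal differs between arms, the exclusion depends on a post-randomisation event and can move the odds ratio. The same analyses are repeated for the China subgroup.

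**Working it through.** **Who is lost.** Protocol 3.1 and Table 5 place TDI, SGRQ and CAT at Visits 4, 6 and 8 (Days 28, 84 and 168). None is on the Early Withdrawal Visit list in Protocol 4.8, and SAP 10.7.1 restricts standalone early-withdrawal data to worst-case summaries. I read the exception as referring to assessments of the same instrument, because the row-building rules in 10.7.2.1 work from that instrument's derived variables. Then:

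- Withdrawn on Day 20: no post-baseline value, no row, absent at every visit.
- Withdrawn on Day 30 after attending Visit 4: non-responder at Days 84 and 168.

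For trough FEV1, a dosed subject with a baseline but no trough from Day 2 onward is 0 under 10.6.5 and has no row under 10.7.2.1. Few subjects can be in that position.

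**The plan's own figure.** Protocol 4.1 expects 18% withdrawal from 192 + 96 = 288: 288 × 0.82 = 236.2, agreeing with the stated 236. By arm, 192 × 0.82 = 157.4 and 96 × 0.82 = 78.7. The documents give no responder rates, no split of withdrawal by arm and no share before Day 28.

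**Illustration.** Assumed: completer response of 50% on UMEC and 35% on placebo; all subjects dosed with a baseline; the same early share in both arms; unadjusted odds ratios. For each arm let N be the number randomised, R the completer responders and E the withdrawals before Day 28.

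- All withdrawals as non-responders: odds = R/(N − R).
- With the exception: odds = R/(N − E − R).

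Equal 18% withdrawal, half of it early:

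- UMEC: R = 157.44 × 0.50 = 78.72; E = 17.28. Placebo: R = 78.72 × 0.35 = 27.55; E = 8.64.
- All as non-responders: (78.72/113.28)/(27.55/68.45) = 1.73.
- Exception: (78.72/96.00)/(27.55/59.81) = 1.78.

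15% against 24% withdrawal (28.8 + 23.04 = 51.84 of 288, again 18%), half early:

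- UMEC: R = 163.2 × 0.50 = 81.6; E = 14.4. Placebo: R = 72.96 × 0.35 = 25.54; E = 11.52.
- All as non-responders: (81.6/110.4)/(25.54/70.46) = 2.04.
- Exception: (81.6/96.0)/(25.54/58.94) = 1.96.

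| Withdrawal, UMEC / placebo | All as non-responders: rates, OR | Exception, a quarter early: OR | Exception, half early: rates, OR |
|---|---|---|---|
| 18% / 18% | 41.0% v 28.7%, 1.73 | 1.75 | 45.1% v 31.5%, 1.78 |
| 15% / 24% | 42.5% v 26.6%, 2.04 | 2.00 | 45.9% v 30.2%, 1.96 |
| 12% / 30% | 44.0% v 24.5%, 2.42 | 2.30 | 46.8% v 28.8%, 2.17 |

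**Why the direction changes.** The exception multiplies each arm's odds by 1/(1 − E/(N − R)). The odds ratio rises if early withdrawals are a larger fraction of the non-responders on UMEC (equal withdrawal: 17.28/113.28 = 0.153 against 8.64/68.45 = 0.126) and falls if they are a larger fraction on placebo (15% / 24%: 14.4/110.4 = 0.130 against 11.52/70.46 = 0.163).

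**The case against.** The strongest reply is that the exception is deliberate and coherent. For TDI, SGRQ and CAT the derivation sections all point to 10.7.2.1, where a specific clause qualifies a general rule, and it agrees with the minimum-data rule in SAP 10.7.1 and its counterpart in Protocol 8.3.5. This stands: for these three endpoints the text can be followed without contradiction. The criticism is of what the rule does.

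A reader might infer a three-way conflict in which the same subject is a non-responder, not imputed, or left out, depending on the section consulted. The documents do not support that. SAP 10.7.2.4 can be read as no further imputation once responder status has been derived, and 10.7.2.1 itself leaves the original dataset untouched and adds rows only to the analysis dataset. So the odds ratio with no imputation at all, (0.50/0.50)/(0.35/0.65) = 1.86 in every row above, is not a rival planned result. The sentence is only unqualified where it should refer to 10.7.2.1. The mismatch that remains, between 10.6.5 and 10.7.2.1, concerns the trough flag and very few subjects.

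It is also fair to say that not every early withdrawal is a treatment failure. Protocol 4.5 also lists consent withdrawal, loss to follow-up, and ECG and laboratory criteria. But 10.7.2.1 already counts such withdrawals as non-responders when they come later, so reason for withdrawal does not justify a different rule before Day 28.

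**Conclusion.** The point holds as a minor one. Followed as written, SAP 10.7.2.1 removes modified ITT subjects who withdraw before their first TDI, SGRQ or CAT assessment and counts later withdrawals as failures. It also departs from the trough rule in 10.6.5.

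In the half-early scenarios the odds ratio moves from 1.73 to 1.78, from 2.04 to 1.96, or from 2.42 to 2.17. These rest on assumed response rates, arm splits and early shares, and none is a forecast. A reader might infer that the exception biases the comparison in a known direction; the documents give no withdrawal split by arm or by time, and the direction reverses across plausible splits.

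SAP 10.11 makes comparisons on secondary and other endpoints exploratory. The primary repeated-measures analysis of trough FEV1, the continuous TDI analysis and the sample size are unaffected.

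**What to change.** - **SAP 10.7.2.1:** keep the missing-baseline condition and delete the clause on subjects without post-baseline assessments. State that for modified ITT subjects with a baseline and no post-baseline assessment, non-responder rows with IMPFLAG 0 are created at every planned responder visit. Deletion alone is not enough, because the present rule adds rows only after a last visit with data, which these subjects do not have.
- **SAP 10.7.1:** state that the minimum-data rule does not apply to responder analyses.
- **SAP 10.7.2 and 10.7.2.4:** say that responder status is as derived in 10.7.2.1, with no further imputation.
- **SAP 10.6.5:** the trough flag then agrees without change.

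The cost is a few lines of SAP text and a few added rows, settled before unblinding. Response rates fall slightly in both arms.
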